5.4 Resources Supplied by the Clinical Site

Staffing

- Principal Investigator and Sub-Investigators, as needed

- Study Coordinator
- Study staff members as needed including phlebotomist
- A data entry person for EDC data entry (Requires Medidata RAVE training)

Other

- Final informed consent documents, and other necessary supporting documents, as appropriate
- IRB submission of protocol and informed consent documents, and other necessary supporting documents, as appropriate
- Computer with internet connection for site access to EDC system
- Wireless internet access
- Facility with adequate space for conducting all testing.
- Approximately 48 subjects who meet enrollment criteria
- Appropriate care/supplies for treating hypoglycemic events if necessary (e.g. nutritional supplements or fast acting glucose tablets/gel)
- Venipuncture supplies
- Measurement of hemoglobin A1c and fructosamine (or send the blood to Central laboratory for these tests)

5.5 Subject Compensation

Subjects will receive nominal compensation for their time and inconvenience as specified in the informed consent form.

6.0 RISK/ BENEFIT ASSESSMENT

Risks Associated with the App

Risks associated with the use of diabetes Apps, which may include some confusion with interpreting the messages shown on the App and inappropriate use of information, could lead to improper management of diabetes.

The App used in this clinical study will not provide any prescriptive advice for diabetes therapy which could be a cause for error in diabetes management. Patients are instructed how to use the information provided by the App appropriate for their diabetes management.

The Contour Diabetes App 2.0 used in this study is an investigational device. But the forerunning Contour Diabetes App 1.0 is CE-marked and has been launched commercially outside the US. The risk management analysis of the Contour Diabetes App 2.0 focuses on any risks related to the additional recognized glucose patterns and smart testing plans implemented in the updated version. While conflicting patterns may be displayed to the user possibly causing confusion in interpretation of the messages, an extensive pattern management algorithm has been incorporated in the system to mitigate this risk and decrease any confusion. Furthermore, the additional smart testing plans included in this update do not add any risks to the device.

Other Known Risks with BGM Use

Risks associated with this study include those associated with obtaining blood from finger and venipuncture.

The following risks are anticipated and will not be reported as Adverse Events (see section 7.0 for further details):

- 1) Bleeding: Mild bleeding similar to being stuck with a pin
- 2) Swelling (Edema): A mild swelling similar to a mosquito bite
- 3) Bruising: Less than one inch across (fingerstick) or 2 inches across (venipuncture)
- 4) Redness (Erythema): Mild reddening or darkening of the skin in the immediate area around the puncture site
- 5) Soreness: Mild discomfort at the puncture site resolving (going away) within one to two days (fingerstick) or within hours (venipuncture)

The following risks are unlikely but possible and will be reported as anticipated Adverse Events:

- 1) Bleeding: Continued bleeding requiring changing a bandage
- 2) Bruising: A worsening bruise that is firm to the touch
- 3) Redness (Erythema): Bright redness or skin darkening spreading across the area (fingerstick) or across the arm (venipuncture)
- 4) Soreness: Worsening pain and/or pain that interferes with activity
- 5) Infection: Bright redness or skin darkening spreading across the area with warmth and/or swelling, and/or red streaking
- 6) Nerve injury: Numbness or shooting pain in the forearm
- 7) Fainting: Dizziness including in extreme cases fainting
- 8) Numbness in the area of the puncture wound
- 9) Subjects should be instructed to report such events to the investigator or designee.

Expected Benefits

This study allows persons with diabetes the opportunity to participate in a study designed to evaluate a new product for use in their home diabetes management. But subjects have no further personal individual benefit from study participation regarding their diabetes therapy. Subjects have the opportunity to gain experience with an app-based diabetes data management under the supervision of an investigator.

Risk-Benefit Evaluation

In this clinical study, subjects will not be administered additional drugs and individual diabetes treatment will not be changed due to the study procedures.

Potential risks for the subjects caused by the use of the investigational Contour Diabetes App 2.0 have been evaluated in a systematic risk assessment procedure. The identified risks (“anticipated adverse events”) were classified to be in the non-critical range and do not exceed the risks described in this chapter.

The risks and burden associated with the participation in this clinical study do not exceed the risk and burden associated with the subjects’ regular diabetes treatment. The subjects have no personal benefit from participating in the study, but will be paid compensation.

The insights obtained in this study will help to understand patients' experiences and needs using app-based diabetes management systems which might eventually help patients with diabetes mellitus to better accomplish their treatment goals.

This study allows persons with diabetes the opportunity to participate in a study designed to evaluate a new product for use in his/her home diabetes management program.

7.0 REPORTING OF ADVERSE EVENTS

The procedures to be conducted under this protocol are considered low risk.

7.1 Description and Classification

7.1.1. An adverse event (AE) during a clinical evaluation is “any untoward medical occurrence, unintended disease or injury, or untoward clinical signs (including abnormal laboratory findings) in subjects, users or other persons, whether or not related to the investigational medical device.” It is not dependent on whether the event is considered to be related to the investigational product or the study. An adverse event includes events not seen at the beginning of the study, or worsened if present at the beginning. Adverse events can be classified as presented in Table 1.

7.1.2. The next classification to consider is whether or not the AE is Anticipated or Unanticipated. In order for an AE to be considered ‘anticipated’ it must be listed in the protocol and ICF prior to any occurrence.

7.1.3. For studies on products that have not yet been cleared for market, it is important that all AE’s be documented and included in the study file.

7.1.4. An unanticipated serious adverse device effect (USADE) is: Any serious adverse effect on health or safety or any life-threatening problem or death caused by, or associated with a device, if that effect, problem or death was not previously identified in nature, severity or degree of incidence in the investigational plan or application (including a supplementary plan or application), or any other unanticipated serious problem associated with a device that relates to the rights, safety or welfare of subjects [MEDDEV 2.7.3].

7.2 Hypoglycemia is defined as having a measured fingerstick (SMBG) or venous glucose result of ≤ 80 mg/dL [3.9 mmol/L] and can be a common occurrence with persons who have diabetes. Hypoglycemic events categorized as severe hypoglycemia will be reported in this trial and will be considered adverse events. Severe hypoglycemia has occurred if the answer is yes to any of the following 3 questions:

1. Did the patient have an episode of suspected hypoglycemia treated with any form of carbohydrate or with glucagon that required the assistance of others to treat?

Note “patient requires the assistance of others to treat” means that neurologic impairment was severe enough to prevent self-treatment in the opinion of those providing assistance to treat.

Assisting a patient out of kindness, when assistance is not required should not be considered as “requiring the assistance of other to treat.”

OR

2. Did the patient lose consciousness during the episode?

OR

3. Did the patient have a seizure during the episode?

If the subject experiences a severe hypoglycemic event it will be considered to be an anticipated AE and will be recorded on the Adverse Event Form by the study staff.

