7.3 Procedure for Reporting an Adverse Event

7.3.1 All adverse events will be documented during this study by completing the Adverse Event Form. The nature of each event and date of onset, outcome, course, maximum intensity and action taken with respect to treatment should be established. Details of any corrective treatment should be recorded on the AE Form. Investigators should follow-up on the status of subjects experiencing an ongoing adverse event until the event has been resolved, or until the condition has stabilized.

Table 1: Classification of Adverse Event

Serious*	Non-Serious

An adverse event that leads to:
 
a) death;
 
b) a serious deterioration in health of the subject that,
 
 1) resulted in a life-threatening illness or injury,
 
 2) resulted in a permanent impairment of a body structure or a body function,
 
 3) required in-patient hospitalization or prolongation of existing hospitalization,
 
 4) resulted in medical or surgical intervention to prevent permanent impairment to body structure or a body function;
 
c) To fetal distress or a congenital abnormality or birth defect.
 
May be anticipated or unanticipated.
 
*EN ISO 14155. Clinical investigation of medical devices for human subjects – Good Clinical Practice
	
All adverse events not reported as serious. At each visit, all adverse events observed by the investigator/designate or reported by subject must be evaluated and recorded on an adverse event form.
 
A non-serious adverse event is further classified with respect to severity and relationship to the trial product. A non-serious adverse event may be anticipated or unanticipated.
 
Further classification with regard to severity
 
 • Mild: Transient symptoms, easily tolerated, no interference with subjects daily activities. • Moderate: Marked symptoms, moderate interference with subjects daily activities, and tolerable. • Severe: Considerable interference with subject’s daily activities, not tolerable.

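### Does the mismatch between 80 mg/dL and 3.9 mmol/L in the hypoglycemia definition change what the trial records or concludes?

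*Combined protocol and SAP*

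**What the plan says.** Section 7.2 opens with the numeric definition: "Hypoglycemia is defined as having a measured fingerstick (SMBG) or venous glucose result of ≤ 80 mg/dL [3.9 mmol/L". After remarking that such events can be common in diabetes, it turns to reporting: "Hypoglycemic events categorized as severe hypoglycemia will be reported in this trial and will be considered adverse events". An event is severe if any one of three questions is answered yes. The first, cut here before its last word, asks "Did the patient have an episode of suspected hypoglycemia treated with any form of carbohydrate or with glucagon that required the assistance of others to". The second asks "Did the patient lose consciousness during the episode" and the third "Did the patient have a seizure during the episode". None of them mentions a glucose value.

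The general adverse event (AE) rules stand on either side of this. Section 7.1.1 defines an AE broadly and includes "untoward clinical signs (including abnormal laboratory findings) in subjects, users or other persons, whether or not related to the investigational medical device". Section 7.3.1 states: "All adverse events will be documented during this study by completing the Adverse Event Form". Table 1 adds that "all adverse events observed by the investigator/designate or reported by subject must be evaluated and recorded on an adverse event form". Section 7.3.2 sends the non-serious AEs to the IRB at closeout.

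**The concern.** A definition in the safety section that gives two values for one limit cannot be applied as written. A whole-number reading from 71 to 80 mg/dL is hypoglycemia by the first figure and not by the second.

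The possible consequence runs through AE recording. Section 7.2 names only severe events as reportable, which invites the inference that non-severe hypoglycemia stays off the AE Form. If the numeric limit says which events belong to that unrecorded group, the unit a staff member reads decides whether a symptomatic, non-severe episode at 75 mg/dL is recorded. The AE list collected at about days 14, 28 and 42, and the closeout report to the IRB, could then differ by reader.

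**Working it through.** **The conversion**

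Inputs: 80 mg/dL and 3.9 mmol/L (Section 7.2). The documents give no conversion factor. I assume k = 18.016 mg/dL per mmol/L, from a molar mass of glucose of 180.16 g/mol, and check the range 18.0 to 18.02.

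- mmol/L = (mg/dL) / k: 80 / 18.016 = 4.44 mmol/L. It is 4.44 across the range of k.
- mg/dL = (mmol/L) × k: 3.9 × 18.016 = 70.26 mg/dL. The range is 70.2 to 70.3.
- Gap: 80 − 70.26 = 9.74 mg/dL, or 4.44 − 3.9 = 0.54 mmol/L.
- Smallest gap if both figures were rounded: 79.5 − 3.95 × 18.016 = 79.5 − 71.16 = 8.34 mg/dL.
- Factor needed for the figures to agree: 80 / 3.9 = 20.5, well outside the range.

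The stated equivalence is not reproduced, and rounding does not rescue it. Ten whole values, 71 to 80 mg/dL, are classed differently (nine, 72 to 80, if readings are first rounded to 0.1 mmol/L).

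**Where the limit is used**

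| Place | What it uses |
|---|---|
| Section 2.0, other objective 2 | Severe events only |
| Section 3.0, safety list | AEs, severe episodes, hospitalizations; no limit |
| Sections 5.1.5 and 5.1.6, safety updates | Severe events and hospitalizations |
| Section 7.2, severity questions | Clinical signs; no glucose value |
| Section 11.0 | Questionnaire scores, changes in HbA1c, fructosamine, weight and insulin, HbA1c against average glucose, utilization rates; no limit |
| Appendix C | Rows for AEs, severe episodes and hospitalizations; no limit |

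Nothing outside the defining sentence applies the number.

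**Could it still decide whether an event is recorded?**

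Take the symptomatic, non-severe episode at 75 mg/dL (75 / 18.016 = 4.16 mmol/L) under the three available readings of Section 7.2.

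1. There is no exemption. The general rules apply and the episode goes on the form under either figure.
2. Among hypoglycemic episodes only severe ones are AEs, and episodes are recognised clinically. The episode stays off the form under either figure.
3. Non-severe events are exempt, and the numeric limit bounds the exemption. The episode is off the form by 80 mg/dL and on it by 3.9 mmol/L.

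Only the third reading makes the unit matter, and it is the weakest. The exemption is not written. Where the protocol does exempt events it says so, in Section 6.0, and that list holds only mild puncture-site effects. Section 7.1.3, Section 7.3.1 and Table 1 call for all AEs to be recorded. The first severity question speaks of suspected hypoglycemia, so Section 7.2 itself does not require a measurement to recognise an episode. The third reading also gives an odd result: under 3.9 mmol/L, a symptomatic episode at 75 mg/dL is recorded while one at 65 mg/dL (3.61 mmol/L) is not.

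No information is lost either. Section 10.0 keeps every meter and manually entered reading in the cloud data, so a count below any limit could be made later.

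**The case for a change.** The strongest case for acting is that this is the protocol's only numeric definition of hypoglycemia, it sits in the safety section, and it is certainly inconsistent. The paragraph can naturally be read as setting ordinary hypoglycemia aside and pulling severe episodes back in. The general AE rules contain no matching exception, so staff are not told expressly what to do with a symptomatic, non-severe low reading. One corrected line and one added sentence would cost almost nothing.

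Two parts of this stand. The figures contradict each other, and the protocol does not expressly say whether non-severe hypoglycemia is an AE. The second point is separate: it would remain with the units corrected, and it asks for detail that the general AE rules already let staff supply.

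What does not stand is the link between the two. Counting readings does not build it. Minimum testing gives 40 × 42 × 2 = 3,360 readings (40 completers, about 42 days, two tests a day), but the share at 71 to 80 mg/dL is not given. Such a count would in any case be of readings, not of AE records. No effect on the AE record has been shown.

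**Conclusion.** The contradiction is real, about 9.7 mg/dL or 0.54 mmol/L for a conversion factor near 18.0, and the two figures in Section 7.2 must be reconciled as an editorial matter. Which value was intended is for the sponsor to say. No change to the plan follows. The severe hypoglycemia definition, the primary endpoint, the secondary endpoints and the Section 11 analyses do not depend on the limit, and an effect on AE recording requires an exemption that the protocol does not state. The silence on non-severe events is a gap in detail. This conclusion assumes that hypoglycemia is reported as the objectives say, as severe events only. If someone later counted low readings from the cloud data, the limit would have to be fixed first, because readings of 71 to 80 mg/dL would be classed differently.

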7.3 Procedure for Reporting an Adverse Event

7.3.1 All adverse events will be documented during this study by completing the Adverse Event Form. The nature of each event and date of onset, outcome, course, maximum intensity and action taken with respect to treatment should be established. Details of any corrective treatment should be recorded on the AE Form. Investigators should follow-up on the status of subjects experiencing an ongoing adverse event until the event has been resolved, or until the condition has stabilized.

Table 1: Classification of Adverse Event

Serious*	Non-Serious

An adverse event that leads to:
 
a) death;
 
b) a serious deterioration in health of the subject that,
 
 1) resulted in a life-threatening illness or injury,
 
 2) resulted in a permanent impairment of a body structure or a body function,
 
 3) required in-patient hospitalization or prolongation of existing hospitalization,
 
 4) resulted in medical or surgical intervention to prevent permanent impairment to body structure or a body function;
 
c) To fetal distress or a congenital abnormality or birth defect.
 
May be anticipated or unanticipated.
 
*EN ISO 14155. Clinical investigation of medical devices for human subjects – Good Clinical Practice
	
All adverse events not reported as serious. At each visit, all adverse events observed by the investigator/designate or reported by subject must be evaluated and recorded on an adverse event form.
 
A non-serious adverse event is further classified with respect to severity and relationship to the trial product. A non-serious adverse event may be anticipated or unanticipated.
 
Further classification with regard to severity
 
 • Mild: Transient symptoms, easily tolerated, no interference with subjects daily activities. • Moderate: Marked symptoms, moderate interference with subjects daily activities, and tolerable. • Severe: Considerable interference with subject’s daily activities, not tolerable.

Relationship to trial product:
 
 • Definitely Related: Causal relationship has been established and documented • Probably Related: Good reasons and sufficient documentation to assume causal relationship have been established • Possibly Related: Causal relationship is likely and cannot be excluded • Probably Not Related: Good reasons and sufficient documentation not established to assume causal relationship • Not Related: The event is most likely related to an etiology other than the trial treatment 	

7.3.2 Reporting of Adverse Events in the US:

1. The Investigator or designee will notify the Study Manager or Monitor within 24 hours of any Serious Adverse Event that occurred during the study. The sponsor will promptly review all information relevant to the safety of the investigational device. The information must be provided by phone or fax to:

[REDACTED]

2. The investigator or designee must notify the sponsor and reviewing IRB by phone or fax of Unanticipated Serious Device-Related Adverse Events within 24 hours of learning of the event, followed by a written report within 10 working days after learning of the event.
3. Upon receipt of a report of an UADE by the Ascensia Diabetes Care Study Manager or Monitor, the report will be immediately forwarded to the Ascensia Diabetes Care Medical Director, [REDACTED] email address: [contact]).
4. The sponsor (Ascensia Diabetes Care) must report Unanticipated Adverse Device Effects (UADE) to the FDA, all participating investigators, and reviewing IRBs within 10 working days after the sponsor first receives notice of the event.
5. Regardless of the above definitions, any additional adverse experience that the investigator considers serious, and/or of concern in relationship to the study must be documented and reported to the Study Manager or Monitor within 24 hours.
6. All non-serious adverse events will be reported to the IRB in the study closeout correspondence to the IRB.

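### Table 1 in section 7.3 calls for a device-relationship grade only for non-serious events and sets Possibly Related too high, so IRB and FDA escalation of serious events has no stated threshold

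*Combined protocol and SAP*

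**What the plan says.** All references are to the combined protocol and SAP.

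- **Who is graded.** Table 1 says: "A non-serious adverse event is further classified with respect to severity and relationship to the trial product". For serious events the only further classification it gives is "May be anticipated or unanticipated".
- **What is established for every event.** Section 7.3.1: "The nature of each event and date of onset, outcome, course, maximum intensity and action taken with respect to treatment should be established". Relationship to the device is not in that list.
- **The scale.** There are five grades, from Definitely Related to Not Related. The third is "Possibly Related: Causal relationship is likely and cannot be excluded" and the fourth is "Probably Not Related: Good reasons and sufficient documentation not established to assume causal relationship".
- **Reporting routes in 7.3.2.** Item 1: "The Investigator or designee will notify the Study Manager or Monitor within 24 hours of any Serious Adverse Event that occurred during the study". Item 2: "The investigator or designee must notify the sponsor and reviewing IRB by phone or fax of Unanticipated Serious Device-Related Adverse Events within 24 hours". Items 3 and 4 take unanticipated adverse device effects to the sponsor's medical director, and then to the FDA, the investigators and the IRBs within 10 working days. Item 5 is a 24-hour catch-all to the study manager or monitor for anything else the investigator thinks serious or worrying. Item 6 sends all non-serious events to the IRB at closeout.
- **A separate standard.** Section 7.1.4 defines an unanticipated serious device effect as one that the device caused or with which it is associated. It does not refer to the five grades.
- **Timing.** Table 1: "At each visit, all adverse events observed by the investigator/designate or reported by subject must be evaluated and recorded". Appendix C marks adverse event capture at about Days 14, 28 and 42, with no mark at Day 0 (Visit 1).

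**The concern.** The scale is required where it changes no reporting route, and is not required where a relatedness judgement decides one. Non-serious events all reach the IRB at closeout whatever their grade. For an unanticipated serious event, the judgement that the device was involved decides whether items 2 to 4 apply, and the protocol assigns neither a scale nor a cut-off to that judgement.

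The wording of the third grade adds a bias. In ordinary use, possibly related means that a cause cannot be ruled out. Here the cause must also be likely. For an investigational app used with a meter to manage insulin-treated diabetes, where section 6.0 itself names improper diabetes management as the app's risk, relatedness grades are part of what the study should report reliably. Grades that lean toward unrelated understate the app's possible contribution, and two investigators reading the same text could escalate the same serious event differently.

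**Working it through.** No arithmetic applies, and the plan gives no figure to reproduce. The check sets the passages side by side.

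**Step 1: where a grade is required.** Table 1 names only non-serious events for relationship grading. Section 7.3.1 lists six items for each event (nature, onset date, outcome, course, maximum intensity, action taken), and none is relationship. So the text requires a grade for non-serious events and is silent for serious ones. This rests on the quoted sentence and not on the table's layout, because the column holding the relationship block cannot be confirmed from the extracted text.

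**Step 2: where relatedness changes a route.** Four cases follow through 7.3.2:

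1. *Non-serious, any grade.* Item 6: IRB at closeout. The grade changes nothing.
2. *Serious, unanticipated, device cause likely.* Item 1 applies, and items 2 to 4 apply on any sensible reading.
3. *Serious, unanticipated, device cause possible but not likely.* Item 1 applies. If the Table 1 scale is borrowed, the event is Probably Not Related and items 2 to 4 would probably not be triggered. If the 7.1.4 standard is used, association with the device may be enough and they would be. The protocol does not say which reading governs.
4. *Serious, anticipated.* Item 1 applies. Items 2 to 4 ordinarily do not, whatever the grade, because they also require the event to be unanticipated. Section 7.2 classes severe hypoglycemia as anticipated, so a hospitalization for it would usually fall here.

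The gap in the escalation rule is therefore case 3. In case 4 a grade would ordinarily not change the route, but the text still does not require one to be recorded.

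**Step 3: whether the five grades fit together.** Possibly Related needs a cause that is likely and also not excludable. An event whose device cause cannot be excluded but is not likely fails the first condition. It also fails the two higher grades, which need established causation or good reasons with documentation. It falls to Probably Not Related, or to Not Related if another cause is most likely. The misplacement runs one way, toward unrelated. Separately, a likely but poorly documented cause meets the wording of both Possibly Related and Probably Not Related, so that boundary is unreliable too.

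**Step 4: Day 0.** Visit 1 includes a blood draw (section 3.0) and a fingertip test (5.1.2), and section 6.0 lists reportable puncture events. Table 1 asks for evaluation at each visit, but Appendix C has no adverse event mark at Day 0. The two should agree.

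**The case against.** A reader might infer that device-related serious harm could go unseen. The documents do not support that. Item 1 of 7.3.2 carries every serious event to the study manager or monitor within 24 hours whatever its cause, with prompt sponsor review of safety information; item 5 catches the rest; and 7.3.1 documents all events. This objection stands and limits the point to grading and to the IRB and FDA routes.

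It can also be said that the Table 1 scale is not the gate for those routes, since 7.1.4 has its own, broader standard and item 2 cannot be followed without some judgement of relatedness. That is fair. What is missing is the link between the two, not any duty to judge causality.

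Two further inferences go too far. One is that serious events will carry no causality grade: the Adverse Event Form is not in the documents and may collect it, so only the protocol text's silence is established. The other is that the fault decides how severe hypoglycemia is escalated: its anticipated status would ordinarily keep it out of items 2 to 4 at any grade.

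Finally, the available text of section 11 plans no table or test by relatedness, so no planned analysis changes. That is correct, but it does not repair the definition of the third grade. The Day 0 point is minor: Table 1 already covers each visit, subjects are to be told to report puncture events, and the contact at about two weeks collects events since Visit 1.

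**Conclusion.** The point holds as one of misgrading and unclear escalation. The protocol text requires a relationship grade only for non-serious events, leaves unanticipated serious events without a stated threshold for items 2 to 4 of 7.3.2, and defines Possibly Related so that possible-but-not-likely cases are graded toward unrelated. The last of these is a wrong rule and not just missing detail.

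The size is one of five grades misdefined, and one class of event (unanticipated, serious, device cause possible but not likely) whose IRB and FDA route depends on which passage is read. The documents give no event counts, so the number of affected events is unknown. No endpoint, hypothesis test or 24-hour notice to the sponsor is affected.

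Two assumptions apply: that the Adverse Event Form does not already settle the matter, and that the adverse device effects of items 3 and 4 are those defined in 7.1.4, although the abbreviations differ.

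**What to change.** 1. State in 7.3.1 and Table 1 that relationship to the device is assessed and recorded for every adverse event, serious and non-serious, including on the 24-hour serious event notice.
2. Remove the requirement of likelihood from Possibly Related, so that it means a causal relationship that cannot be excluded. Then reread the two lower grades so that the five do not overlap.
3. State which grades count as device-related for items 2 to 4 of 7.3.2, consistent with the caused-or-associated standard of 7.1.4.
4. Minor: mark adverse event capture at Day 0 in Appendix C, to agree with Table 1.

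The cost is a few lines of text, one mark in the schedule and at most one form field. The downside is that a few more events may be graded possibly related.
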